### 1. RCT Details

This section provides a high-level overview of a **published** RCT that the described real-world evidence study is trying to replicate as closely as possible given the remaining limitations inherent in the healthcare databases.

### 1.1 Title

### Oral Rivaroxaban for Symptomatic Venous Thromboembolism (EINSTEIN DVT)

### 1.2 Intended aim(s)

To compare the risk of symptomatic, recurrent venous thromboembolism (VTE) in patients with acute, symptomatic deep vein thrombosis (DVT) for rivaroxaban versus standard therapy of warfarin.

#### 1.3 Primary endpoint for replication

The primary outcome of the study was symptomatic, recurrent VTE

# 1.4 Required power for primary endpoint and noninferiority margin (if applicable) Assuming a noninferiority margin of 2.0, it was determined that about 3,000 patients would be needed to achieve 90% power to conclude noninferiority of rivaroxaban over standard therapy at two-sided alpha of 0.05.

1.5 Secondary endpoint for replication (assay sensitivity) and RCT finding Major bleeding; RR = 0.65 (95% CI 0.33–1.30)

### 1.6 Trial estimate

RR = 0.68 (95% CI 0.44-1.04) comparing rivaroxaban vs standard therapy (Agnelli et al., 2010)

### 2. Person responsible for implementation of replication in Aetion

[name] implemented the study design in the Aetion Evidence Platform. She is not responsible for the validity of the design and analytic choices. All implementation steps are recorded and the implementation history is archived in the platform.

### 3. Data Source(s)

[figure not shown]
Optum, MarketScan, Medicare

Effectiveness research with Real World Data to support FDA's regulatory decision making

### 4. Study Design Diagram

The study design diagram visualizes key aspects of the longitudinal study design for expedited review.

Figure 1.

### 5. Cohort Identification

#### 5.1 Cohort Summary

This study will involve a new user, parallel group, propensity score-matched, retrospective cohort study design comparing rivaroxaban to warfarin users. The patients will be required to have continuous enrollment during a baseline period of 180 days before initiation of rivaroxaban or warfarin (index date). We will restrict the analyses to patients with a diagnosis of proximal DVT without symptomatic PE.

#### 5.2 Important steps for cohort formation

New use of rivaroxaban, exposure, and warfarin, comparator, is defined as no use of either therapy in 180 days prior to index date.

#### 5.2.1 Eligible cohort entry dates

Market availability of rivaroxaban in the U.S. prevention of venous thromboembolism after orthopedic surgery started on July 30, 2008

- For Medicare: July 30, 2008– December 31, 2017 (end of available data)
- For Marketscan: July 30, 2008 December 31, 2018 (end of available data)
- For Optum: July 30, 2008 March 31, 2020 (end of available data)

### 5.2.2 Specify inclusion/exclusion criteria for cohort entry and define the index date. Inclusion and exclusion criteria were adapted from the trial as closely as possible. Definitions for all inclusion/exclusion are provided in **Appendix A** and are summarized in the flowcharts below.

#### 5.3 Flowchart of the study cohort assembly

	Optum		Truven		Medicare	
	Less Excluded Patients	Remaining Patients	Less Excluded Patients	Remaining Patients	Less Excluded Patients	Remaining Patients
All patients		77,673,639		200,203,908		6,886,908

Final cohort		11353		17885		49367
Excluded based on Exclusion # 15 - Symptomatic Pulmonary Embolism	-369	11,353	-817	17,885	-1008	49,367
Excluded based on Exclusion # 14 - CYP3A4 Inhibitors	-12	11,722	-28	18,702	-72	50,375
Excluded based on Exclusion # 11 - Malignant Hypertension and based on Exclusion # 12 - Pregnancy	-39	11,734	-116	18,730	-120	50,447
Excluded based on Exclusion # 10 - Active Bleeding/High Risk for Bleeding	-295	11,773	-478	18,846	-1,156	50,567
Excluded based on Exclusion # 9 - CCI	-184	12,068	-155	19,324	-348	51,723
Excluded based on Exclusion # 7 - Liver Disease and based on Exclusion # 8 - Bacterial Endocarditis	-497	12,252	-767	19,479	-1,320	52,071
Excluded based on Exclusion # 6 - CKD stage 4/5/ESRD	-114	12,749	-121	20,246	-496	53,391
Excluded based on Exclusion # 3 - other indications for VKA	-1721	12,863	-2,053	20,367	-9,815	53,887
Excluded based on Exclusion # 2 - Thrombobectomy, Caval Filter	-210	14,584	-335	22,420	-903	63,702
Excluded based on Inclusion # 1 - DVT w/o Symptomatic PE and based on Exclusion # 1 - Age <=18	-117,812	14,794	-168,633	22,755	-499,609	64,605
Excluded based on Use of other NOACs (dabigatran, apixaban, edoxaban)	-5421	132,606	-4267	191,388	-21987	564,214
Excluded based on Gender	0	138,027	0	195,655	0	586,201
Excluded based on Age (missing)	0	138,027	0	195,655	-214	586,201
Excluded based on Age (<65 - Medicare only)	-	-	-	-	-72456	586,415
Excluded due to prior use of exposure and because patient qualified in >1 exposure category	-221,490	138,027	-216,501	195,655	-834,065	658,871
Excluded due to prior use of referent	-516,528	359,517	-684,176	412,156	-3,197,338	1,492,936
Excluded due to insufficient enrollment	-118,721	876,045	-99,207	1,096,332	-232,358	4,690,274
Did not meet cohort entry criteria	-76,678,873	994,766	-199,008,369	1,195,539	-1,964,276	4,922,632

#### 6. Variables

#### 6.1 Exposure-related variables:

#### Study drug:

The study exposure of interest is initiation of rivaroxaban. New initiation will be defined by no use of rivaroxaban or warfarin in the prior 6 months before treatment initiation (washout period).

### Comparator:

New initiators of warfarin, defined by no use of rivaroxaban or warfarin in the prior 6 months.

#### 6.2 Covariates:

- Age
- Sex
- Combined Comorbidity Index (CCI), measured over the baseline covariate assessment period, defined as 180 days prior to and including index date

Covariates listed above represent only a small subset of covariates that will ultimately be controlled for in the design and analysis. We use the covariates above only for initial feasibility analyses to judge whether there is likely to be sufficient overlap between treatment groups to proceed with the study. Remaining covariates are defined only after the study has passed the initial feasibility analysis and the initial power assessment and are listed in Table 1 (**Appendix B**).

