#### 6.3.2 Study follow-up

Both as-treated (AT) and intention-to-treat (ITT) analyses will be conducted with treatment defined as the index drug on the day of cohort entry. Because adherence in the real-world databases is expected to be much worse than in the trial, the AT analysis is the primary analysis, as it targets the relative hazard of outcomes on treatment.

For the AT analyses, the follow-up will start the day after initiation of rivaroxaban and comparator and will continue until the earliest date of the following events:

- The first occurrence of the outcome of interest, unless otherwise specified for selected outcomes,
- The date of end of continuous registration in the database,
- End of the study period,
- Measured death event occurs,
- Nursing home admission
  - Nursing home admissions are considered a censoring event because the data sources utilized typically provide little to no data on a patient, particularly on drug utilization, after admission. We will utilize this as an exclusion reason for cohorts for the same reason.
- The date of drug discontinuation, defined as the date of the last continuous treatment episode of the index drug (rivaroxaban and comparator) plus a defined grace period (i.e., 10 days after the end of the last prescription's days' supply in main analyses).
- The date of augmentation or switching from exposure to comparator or vice versa or augmentation/switching to any other NOAC (e.g. switching from rivaroxaban to apixaban would be a censoring event);
  - $\circ~$  A dosage change on the index treatment does not fulfill this criterion
  - o An added treatment that is not part of the exposure or comparator group does not fulfill this criterion

For the intention-to-treat (ITT) analyses, the censoring based on the augmentation/switching and treatment discontinuation will be replaced with a maximum allowed follow-up time of 365 days.

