### Date conducted: 12/23/20

After review of initial feasibility and power analyses, complete creation of the remaining covariates from Section 6.2. Again, using the dummy outcome of a 90-day gap in database enrollment, complete a 1:1 PS-matched analysis. The PS should include the complete list of covariates.

• Provide plot of PS distributions stratified by treatment group.

Note- Please refer to **Appendix B**.

• Report covariate balance after matching.

Note- For Table 1, please refer to **Appendix B**.

	Overall	Referent	Exposure
Dummy outcome	326 (1.04%)	175 (1.11%)	151 (0.96%)
Death	698 (2.22%)	345 (2.20%)	353 (2.25%)
Start of an additional exposure	1,548 (4.93%)	983 (6.26 %)	565 (3.60%)
End of index exposure	23,549 (74.98%)	11,297 (71.94%)	12,252 (78.02%)
Specified date reached	1,374 (4.37%)	711 (4.53%)	663 (4.22%)
End of patient enrollment	925 (2.95%)	503 (3.20%)	422 (2.69%)
Switch to other NOACs (for censoring) + nursing home admission	2,988 (9.51%)	1,690 (10.76%)	1,298 (8.27%)

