DM Medications - Insulin Copy; n (%)	441 (5.9%)	217 (5.5%)	0.02	779 (5.6%)	196 (5.0%)	0.03	1,692 (5.2%)	734 (4.4%)	0.04	2912 (5.4%)	1147 (4.7%)	0.03
Use of Low Intensity Statins; n (%)	1,617 (21.8%)	763 (19.4%)	0.06	2,357 (16.9%)	521 (13.3%)	0.10	9,199 (28.2%)	4,445 (26.5%)	0.04	13173 (24.4%)	5729 (23.3%)	0.03
Use of High Intensity Statins; n (%) Malignant hypertension; n (%)	769 (10.4%) 771 (10.4%)	503 (12.8%) 206 (5.2%)	-0.08 0.19	1,328 (9.5%) 6,113 (43.7%)	365 (9.3%) 1,154 (29.5%)	0.01	4,205 (12.9%) 13,959 (42.8%)	2,477 (14.8%) 4,636 (27.7%)	-0.06 0.32	6302 (11.7%) 20843 (38.6%)	3345 (13.6%) 5996 (24.4%)	-0.06
	29 (0.4%)	** (0.2%)	0.19	6,113 (43.7%) 51 (0.4%)	1,154 (29.5%) 15 (0.4%)	0.00	13,959 (42.8%)	4,036 (27.7%) 81 (0.5%)	0.00	20843 (38.6%) 254 (0.5%)	5996 (24.4%) #VALUE!	#VALUE!
Cardiovascular stress test; n (%) Echocardiogram; n (%)	29 (0.4%) 1,217 (16.4%)	712 (18.1%)	-0.05	2,591 (18.5%)	15 (0.4%) 783 (20.0%)	-0.04	174 (0.5%) 6,200 (19.0%)	81 (0.5%) 3,177 (19.0%)	0.00	254 (0.5%) 10008 (18.5%)	#VALUE! 4672 (19.0%)	#VALUE! -0.01
Number of BNP tests	1,217 (10.470)	/ 12 (10.1/0)	-0.03	2,331 (10.3%)	/03 (20.0%)	-0.04	0,200 (15.0%)	3,177 (13.076)	0.00	10000 (10.3%)	4072 (15.0%)	-0.01
mean (sd)	0.06 (0.28)	0.11 (0.38)	-0.15	0.03 (0.20)	0.05 (0.25)	-0.09	0.09 (0.33)	0.12 (0.37)	-0.09	0.07 (0.29)	0.11(0.36)	-0.12
Number of Cardiac biomarkers tests (tropnin, CK-MBs, Myo	oglobin, CPK)											
mean (sd)	0.32 (1.21)	0.40 (1.19)	-0.07	0.22 (0.95)	0.28 (1.06)	-0.06	0.22 (0.55)	0.27 (0.62)	-0.09	0.23 (0.79)	0.29 (0.82)	0.00
Number of Ambulatory Blood pressure monitoring tests												
mean (sd)	0.00 (0.04)	0.00 (0.00)	0.00	0.00 (0.04)	0.00 (0.04)	0.00	0.00 (0.03)	0.00 (0.04)	0.00	0.00 (0.03)	0.00 (0.04)	0.00
N of days on antihypertensive medications during baseline							0	0				
mean (sd)	: 78.67 (79.06)	79.51 (80.27)	-0.01	67.34 (78.33)	58.24 (75.77)	0.12	107.82 (76.83)	104.35 (78.11)	0.04	93.34 (77.53)	93.04 (78.09)	0.00
N of days in database anytime prior	70.07 (75.00)	75.51 (00.27)	-0.01	07.54(70.55)	56.24 (75.77)	0.12	107.02 (70.03)	104.33 (70.11)	0.04	55.54 (77.55)	55.04 (78.05)	0.00
mean (sd)	1,629.27 (1,170.61)	1,681.72 (1,331.40)	-0.04	1,747.51 (1,223.63)	2,037.38 (1,445.60)	-0.22	619.84 (384.70)	645.09 (368.82)	-0.07	1050.22 (815.43)	1032.36 (841.75)	0.00
	,	,		,	,			(		(()		
Mean Copay for per prescription cost (charges in U.S. \$) (18	80-1 day prior)						0	0				

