desirudin, argatroban); n (%)	0 (0.0%)	0 (0.0%)	#DIV/0!	0 (0.0%)	0 (0.0%)		0 (0.0%)	0 (0.0%)		0 (0.0%)		#DIV/0!
Use of Ticagrelor ON CED; n (%)	** (0.0%)	** (0.1%)	-0.04	** (0.0%)	** (0.1%)	-0.04	** (0.0%)	** (0.0%)	#DIV/0!	#VALUE!	#VALUE!	#VALUE!
Use of Ticagrelor; n (%)	** (0.0%)	** (0.1%)	-0.04	** (0.1%)	** (0.1%)	0.00	24 (0.1%)	22 (0.1%)	0.00	#VALUE!	#VALUE!	#VALUE!
Number of D-dimer tests												
mean (sd)	0.06 (0.27)	0.11 (0.36)	-0.16	0.06 (0.26)	0.07 (0.29)	-0.04	0.08 (0.30)	0.11 (0.34)	-0.09	0.07 (0.29)	0.10 (0.34)	0.00
Numbe of CRP, high-sensitivity CRP tests												
mean (sd)	0.14 (0.66)	0.18 (0.85)	-0.05	0.12 (0.62)	0.17 (0.72)	-0.07	0.15 (0.72)	0.17 (0.67)	-0.03	0.14 (0.69)	0.17(0.71)	0.00
Number of PT or aPTTt tests							,				,	
mean (sd)	1.04 (2.19)	0.96 (1.60)	0.04	0.72 (1.79)	0.70 (1.51)	0.01	0.62 (1.10)	0.61 (0.89)	0.01	0.70 (1.49)	0.68 (1.15)	0.00
Number of Bleeding time tests	1.04 (2.15)	0.50(1.00)	0.04	0.72 (1.75)	0.70(1.51)	0.01	0.02 (1.10)	0.01 (0.05)	0.01	0.70 (1.45)	0.00(1.15)	0.00
	0.00(0.00)	0.00(0.00)	0.00	0.00(0.03)	0.00(0.00)	0.00	0.00 (0.00)	0.00(0.00)	0.00	0.00(0.00)	0.00(0.02)	0.00
mean (sd)	0.00 (0.02)	0.00 (0.00)	0.00	0.00 (0.03)	0.00 (0.03)	0.00	0.00 (0.02)	0.00 (0.02)	0.00	0.00 (0.02)	0.00 (0.02)	0.00
HAS-BLED Score (ICD-9 and ICD-10), 180 days												
mean (sd)	2.86 (1.05)	2.80 (1.04)	0.06	2.41 (1.01)	2.32 (0.98)	0.09	3.46 (0.81)	3.40 (0.82)	0.07	3.11 (0.90)	3.13 (0.89)	0.00
N of Generic name drugs												
mean (sd)	18.04 (16.90)	16.55 (17.28)	0.09	14.06 (11.77)	13.04 (12.54)	0.08	19.33 (15.03)	17.38 (15.17)	0.13	17.79 (14.54)	16.56 (15.15)	0.00
N of Brand name drugs												
mean (sd)	3.33 (5.27)	3.81 (4.55)	-0.10	3.46 (4.75)	3.79 (3.90)	-0.08	3.58 (5.38)	4.07 (4.63)	-0.10	3.51 (5.21)	3.98 (4.51)	0.00
Use of clopidogrel ; n (%)	295 (4.0%)	130 (3.3%)	0.04	556 (4.0%)	126 (3.2%)	0.04	2,006 (6.1%)	928 (5.5%)	0.03	2857 (5.3%)	1184 (4.8%)	0.02
Systemic embolism; n (%)	263 (3.5%)	100 (2.5%)	0.06	764 (5.5%)	191 (4.9%)	0.03	834 (2.6%)	367 (2.2%)	0.03	1861 (3.4%)	658 (2.7%)	0.04
DVT: n (%)	7,411 (100.0%)	3,936 (99.9%)	0.04	13,970 (99.9%)	3,906 (99.9%)	0.00	32,605 (100.0%)	16,737 (99.9%)	0.04	53986 (100.0%)	24579 (99.9%)	0.04
	21 (0.3%)	13 (0.3%)	#DIV/0!	21 (0.2%)	14 (0.4%)	#DIV/0!	87 (0.3%)	28 (0.2%)	#DIV/0!	21 (0.2%)	14 (0.4%)	-0.04
Post-thrombotic syndrome; n (%)												
PE; n (%)	575 (7.8%)	410 (10.4%)	-0.09	570 (4.1%)	233 (6.0%)	-0.09	1,930 (5.9%)	1,268 (7.6%)	-0.07	3075 (5.7%)	1911 (7.8%)	-0.08

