Number of Bleeding time tests												
mean (sd)	0.00 (0.00)	0.00 (0.00)	#DIV/0!	0.00 (0.03)	0.00(0.03)	0.00	0.00 (0.02)	0.00 (0.02)	0.00	0.00 (0.02)	0.00 (0.02)	0.00
HAS-BLED Score (ICD-9 and ICD-10), 180 days	0.00 (0.00)	0.00 (0.00)	#01070:	0.00 (0.03)	0.00 (0.03)	0.00	0.00 (0.02)	0.00 (0.02)	0.00	0.00 (0.02)	0.00(0.02)	0.00
mean (sd)	2.89 (1.02)	2.93 (1.07)	-0.04	2.37 (1.00)	2.37 (0.99)	0.00	3.49 (0.82)	3.48 (0.81)	0.01	3.17 (0.89)	3.17 (0.89)	0.00
	2.89 (1.02)	2.95 (1.07)	-0.04	2.37 (1.00)	2.37 (0.99)	0.00	3.49 (0.82)	5.48 (0.81)	0.01	3.17 (0.89)	3.17 (0.89)	0.00
N of Generic name drugs												
mean (sd)	18.54 (17.31)	18.70 (19.99)	-0.01	13.69 (11.34)	13.71 (12.94)	0.00	18.66 (14.45)	18.74 (16.05)	-0.01	17.54 (14.21)	17.61 (15.96)	0.00
N of Brand name drugs												
mean (sd)	3.61 (6.03)	3.61 (4.03)	0.00	3.54 (5.26)	3.63 (3.55)	-0.02	3.99 (6.55)	3.97 (4.25)	0.00	3.84 (6.22)	3.85 (4.08)	0.00
Use of clopidogrel ; n (%)	60 (3.8%)	63 (4.0%)	-0.01	91 (3.1%)	100 (3.4%)	-0.02	539 (6.3%)	543 (6.4%)	0.00	690 (5.3%)	706 (5.4%)	0.00
Systemic embolism; n (%)	62 (3.9%)	53 (3.4%)	0.03	145 (5.0%)	156 (5.4%)	-0.02	216 (2.5%)	210 (2.5%)	0.00	423 (3.3%)	419 (3.2%)	0.01
DVT; n (%)	1,575 (100.0%)	1,575 (100.0%)	#DIV/0!	2,897 (99.9%)	2,898 (100.0%)	-0.04	8,504 (99.9%)	8,503 (99.9%)	0.00	12976 (99.9%)	12976 (99.9%)	0.00
Post-thrombotic syndrome; n (%)	** (0.3%)	** (0.3%)	#DIV/0!	** (0.2%)	** (0.2%)	#DIV/0!	23 (0.3%)	20 (0.2%)	#DIV/0!	** (0.2%)	** (0.2%)	0.00
PE; n (%)	163 (10.3%)	158 (10.0%)	0.01	141 (4.9%)	132 (4.6%)	0.01	599 (7.0%)	612 (7.2%)	-0.01	903 (7.0%)	902 (6.9%)	0.00
Coagulation defects; n (%)	43 (2.7%)	46 (2.9%)	#DIV/0!	110 (3.8%)	110 (3.8%)	#DIV/0!	159 (1.9%)	141 (1.7%)	#DIV/0!	110 (3.8%)	110 (3.8%)	0.00
congulation deletes, in (x)	40 (21770)	40 (2.576)		110 (0.070)	110 (5.670)		100 (1.070)	141 (1.776)		110 (0.070)	110 (5.070)	0.00
Diabetes: 1 inpatient or 2 outpatient claims within 18	391 (24.8%)	393 (25.0%)	0.00	516 (17.8%)	543 (18.7%)	-0.02	2,342 (27.5%)	2,351 (27.6%)	0.00	3249 (25.0%)	3287 (25.3%)	-0.01
		,		,	• •• (=••••)		_, (,	_,(			,	
Intracranial or retroperitoneal hemorrhage: 1 inpatier	** (0.1%)	** (0.1%)	0.00	0 (0.0%)	0 (0.0%)	#DIV/0!	12 (0.1%)	10 (0.1%)	0.00	#VALUE!	#VALUE!	#VALUE!
Peptic Ulcer Disease; n (%)	399 (25.3%)	407 (25.8%)	-0.01	574 (19.8%)	571 (19.7%)	0.00	2,559 (30.1%)	2,560 (30.1%)	0.00	3532 (27.2%)	3538 (27.2%)	0.00

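### The covariate window includes the index date and the brand and generic drug counts in the propensity score have no stated exception, so as written they contain the study drug's own fill

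*Combined protocol and SAP*

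**What the plan says.** Section 6.2 describes the comorbidity index as "measured over the baseline covariate assessment period, defined as 180 days prior to and including index date". The wording sits in that one bullet, but it defines a named period and is the only general covariate window in the plan. The section then says: "Remaining covariates are defined only after the study has passed the initial feasibility analysis and the initial power assessment and are listed in Table 1".

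The baseline table in Appendix B lists "N of Brand name drugs" and "N of Generic name drugs" below the heading that marks variables for the PS. Neither row gives a window, says whether it counts fills or distinct products, or says whether the study drugs are left out. The row "Mean Copay for per prescription cost" does carry its own window, ending one day before index. Section 9 instructs: "The PS should include the complete list of covariates".

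Two other rules bear on the point. New use "is defined as no use of either therapy in 180 days prior to index date" (Section 5.2), so the index fill is the only way the study drug can enter a 180-day count. In Section 6.3.2, "the follow-up will start the day after initiation of rivaroxaban and comparator", so the index day belongs to baseline and not to follow-up.

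**The concern.** The index date is the day the study drug is started. A drug count that includes that day gains one unit from the treatment itself, and the unit falls in a different count by arm. Appendix A gives rivaroxaban's brand name as Xarelto, so its index fill would add to the brand count. A warfarin index fill would add mainly to the generic count if warfarin is mostly dispensed as generic.

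A PS fitted on such counts tends to equalize totals that contain the exposure. Mean use before index would then differ between arms while Table 1 prints a difference near zero. The people whom Section 10 asks to approve balance could not see this from the table.

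**Working it through.** **Inputs.** Means (SD) come from the PS-matched Table 1 in Appendix B. W is warfarin, R is rivaroxaban.

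**Formula.** SMD = (mean_W − mean_R) / D, with D = sqrt((SD_W² + SD_R²) / 2).

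**Step 1: reproduce the printed values. Step 2: remove one index fill**, from the brand mean for rivaroxaban and from the generic mean for warfarin. The SDs are held fixed, which is exact if every patient loses one unit.

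Brand count:

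| | W | R | D | Printed | Recomputed | One fill removed |
|---|---|---|---|---|---|---|
| Optum | 3.61 (6.03) | 3.61 (4.03) | 5.13 | 0.00 | 0.000 | (3.61 − 2.61)/5.13 = 0.195 |
| MarketScan | 3.54 (5.26) | 3.63 (3.55) | 4.49 | -0.02 | -0.020 | (3.54 − 2.63)/4.49 = 0.203 |
| Medicare | 3.99 (6.55) | 3.97 (4.25) | 5.52 | 0.00 | 0.004 | (3.99 − 2.97)/5.52 = 0.185 |
| Pooled | 3.84 (6.22) | 3.85 (4.08) | 5.26 | 0.00 | -0.002 | (3.84 − 2.85)/5.26 = 0.188 |

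Generic count:

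| | W | R | D | Printed | Recomputed | One fill removed |
|---|---|---|---|---|---|---|
| Optum | 18.54 (17.31) | 18.70 (19.99) | 18.70 | -0.01 | -0.009 | (17.54 − 18.70)/18.70 = -0.062 |
| MarketScan | 13.69 (11.34) | 13.71 (12.94) | 12.17 | 0.00 | -0.002 | (12.69 − 13.71)/12.17 = -0.084 |
| Medicare | 18.66 (14.45) | 18.74 (16.05) | 15.27 | -0.01 | -0.005 | (17.66 − 18.74)/15.27 = -0.071 |
| Pooled | 17.54 (14.21) | 17.61 (15.96) | 15.11 | 0.00 | -0.005 | (16.54 − 17.61)/15.11 = -0.071 |

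**Step 3: vary the warfarin assumption.** The documents give no brand share for warfarin. If a share w of its index fills is brand, the brand SMD is [(mean_W − w) − (mean_R − 1)] / D, again with the SDs held fixed:

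- w = 10%: pooled (3.74 − 2.85)/5.26 = 0.169; by database 0.167 to 0.181.
- w = 25%: pooled (3.59 − 2.85)/5.26 = 0.141; by database 0.139 to 0.147.
- w = 50%: pooled (3.34 − 2.85)/5.26 = 0.093; by database 0.091 to 0.097.

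**Step 4: vary the number of units counted.** At half a unit per patient the brand SMD is 0.091 to 0.097 by database; at two units it is 0.366 to 0.426.

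**Step 5: distinct medications.** Both arms lose one unit, so the difference does not move (pooled 9.68 against 9.65, printed 0.01).

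**Step 6: does the unmatched table fit?** In Optum, MarketScan and Medicare respectively, rivaroxaban users have fewer generics (by 1.49, 1.02, 1.95) and fewer distinct medications (by 0.50, 0.43, 0.61), but more brand drugs (by 0.48, 0.33, 0.49). Taking one brand unit from rivaroxaban turns the brand gap to 0.52, 0.67 and 0.51 in the other direction, the same direction as the other two counts. That is consistent with a counted index fill but does not prove it.

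A separate table error, not used here: the pooled unmatched SMDs for the brand and generic rows are printed as 0.00 but recompute to -0.096 and 0.083.

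**The case against.** The strongest reply is that nothing in the documents says the two counts include the index fill. The Section 6.2 wording is attached to the comorbidity index, in a list meant for feasibility. Windows are set item by item elsewhere:

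- Copay stops at day -1, the frailty score uses 365 days and the diabetes row 183 days.
- Ticagrelor has one row labelled ON CED (apparently the cohort entry date) and another without that label.
- Some Appendix A exclusions include the initiation day and others do not.
- Section 5.1 describes the enrollment baseline as the 180 days before initiation.

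The design diagram and the linked code folder, neither of which could be consulted, may settle the matter. The unmatched brand gap is also 0.33 to 0.49, not a full unit, and real prescribing differences could produce the pattern in Step 6.

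Much of this stands. A reader might infer three stronger things that the documents do not support:

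- **That the counts are shown to contain the study drug.** They are not. The text permits this as its default reading, and no row or note confirms it or rules it out.
- **That each rivaroxaban patient is paired with a warfarin patient who has one more prior brand fill.** Matching is on a PS built from a long covariate list, so only a difference in group means follows.
- **That the hazard ratio is biased by a known amount.** No effect on it can be derived. Related measures are balanced after matching: comorbidity index 0.02 pooled, commercial against Medicare Advantage 0.00 pooled, and pre-index copay -0.02 to 0.00 by database.

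What does not stand is the idea that item-by-item windows remove the problem. The copay row shows that an exception was written where one was meant. These two rows have none, so the only general window applies to them.

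**Conclusion.** The point holds as a defect in the plan as written. The general window includes the index date, two PS covariates whose index-day content differs by arm have no exception, and the documents leave open whether rivaroxaban and warfarin were removed.

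If one index fill per patient is counted, with rivaroxaban as brand and warfarin as generic, the matched pre-index brand SMD is about 0.19 pooled against a printed 0.00. That exceeds 0.10, a common convention; the plan sets no threshold of its own. It would fall below 0.10 only if about half of warfarin index fills were brand, or if the count held about half a unit per patient. The generic SMD stays at -0.06 to -0.08, and distinct-medication balance is unaffected. If the study drugs are already excluded, the printed balance stands and only the wording needs correcting.

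**What to change.** State in Section 6.2 that the brand and generic drug counts are measured on days -180 to -1, or that rivaroxaban and warfarin are excluded from them, and confirm how the current counts were built. If they include the index fill, refit the PS, rematch, and reissue Table 1 before any outcome analysis. The distinct-medication count needs no change on this ground.

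The cost is one sentence and, if needed, one re-run of the PS and match, with a matched N that may differ slightly from the present 12,985 per arm. Section 13 records no date for the comparative analyses and Section 9 uses a dummy outcome, so the correction can be made without sight of outcomes by arm.
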